1 BACKGROUND

1.1 Overview of Overview of Clinical Studies

[figure not shown]
Binge drinking is a major health issue for men who have sex with men (MSM) at high-risk for acquiring or transmitting HIV. In the National HIV Behavioral Surveillance (NHBS) survey, 84% of MSM consumed alcohol in the past 30 days, and 57% reported at least one occasion of binge drinking.³ The prevalence of binge drinking for MSM is 3.5 times the prevalence in the general US adult population.¹ **The high rates of alcohol use in MSM have been observed for decades and these rates will likely persist.¹⁵⁻¹⁷** In San Francisco, 72% and 55% of MSM reported binge drinking in the past 12 months, and the past 30 days, respectively.¹⁸ Binge drinking is by far the most prevalent exposure attributed to HIV infections among MSM and it is estimated that there are 48,070 binge-drinking MSM in San Francisco.^{19, 20} **MSM are disproportionately impacted by HIV**, accounting for 61% of new infections in 2009.²¹ For San Francisco MSM, HIV prevalence is estimated at 22.7% and HIV annual incidence is estimated at 1.27% per year.²² It is imperative to develop more evidence-based HIV-prevention interventions that are not only efficacious, but also feasible and acceptable to MSM.

Binge and other heavy drinking patterns are associated with HIV risk behaviors. NHBS data show that alcohol use before or during unprotected sex was common for MSM—41% and 43% of alcohol drinkers surveyed reported unprotected insertive and unprotected receptive anal sex while intoxicated on alcohol, respectively, during their most recent sexual episode.³ Similarly, in Project Mix, one of the largest randomized controlled trials of MSM in the US, 40% of current drinkers reported having unprotected sex while intoxicated during their most recent anal sex episode.²³ **Interventions that can be utilized within the risk environment may be more efficacious at reducing HIV risk in this highly impacted population.** Alcohol use is deeply entwined with social activities of MSM¹⁵ and although drinking, *per se*, does not always predict unprotected intercourse, certain risk contexts are more consistently associated with alcohol use.^{4, 24} The acute effects of alcohol consumption (e.g., altered cognition, impaired judgment and increased sexual desire and confidence) may contribute to risk-taking behaviors.²⁵⁻²⁸ A myriad of psychosocial factors (e.g., cognitive escape, impulsivity, expectancies) are believed to mediate the association between alcohol and sexual risk behaviors.^{26, 29-34} Furthermore, bar and club venues frequented by MSM provide conducive environments for both meeting sexual partners and binge drinking.¹²⁻¹⁵ **Notably, event-level analyses of alcohol use immediately before or during sexual episodes in two separate systematic reviews consistently found that binge drinking is independently associated with increased likelihood of having unprotected sex.^{4, 5}** According to event-level analyses for 1,712 HIV-negative MSM, compared to non-binge drinkers, binge drinkers had three times the likelihood of having unprotected sex with non-primary partners.³⁵ These *event-level* assessments of alcohol use provide the most precise temporal link between these two behaviors and provide stronger evidence for causality.^{5, 24} Binge drinking and other patterns of heavy alcohol use are independently associated with a variety of high-risk behaviors in MSM, including unprotected anal sex, multiple partners, and having HIV-serodiscordant partners^{17, 35-44}—a link also observed among black, Native American, and older MSM.⁴⁵⁻⁴⁷ **Binge-drinking and heavy alcohol consumption are major causes of incident HIV infections in MSM.** Binge alcohol use was independently associated with a greater than three-fold increase in odds for new HIV diagnoses among MSM who had a previously (past 12 months) negative HIV-test in a case-control study.⁴⁸ In the Explore study of 4,295 HIV-negative MSM from six metropolitan areas, 29% of HIV incidence was attributable to use of alcohol or other drugs before sex; 6.1% was attributable to heavy alcohol use.⁷ Similarly, in the Multicenter AIDS Cohort Study of 3725 HIV-negative MSM, the hazard for seroconversion among heavy drinkers was 61% greater, compared to those who abstained from alcohol during the 24 year follow-up (1984-2008).⁴⁹

Behavioral interventions to address binge drinking to date have failed to reach MSM. Novel interventions are needed for MSM who binge drink.⁸ Because excessive alcohol use is nearly ubiquitous among MSM and is commonly associated with high-risk sexual behavior and HIV infection, interventions that reduce alcohol consumption are likely to have an impact on the transmission of HIV. The primary prevention approaches to binge drinking for MSM are therapy and alcohol treatment programs. Individual⁵⁰ and couples⁵¹ behavioral therapy approaches have been shown to reduce heavy alcohol use among MSM. However, only 20% of MSM who use alcohol or non-injection drugs have ever participated in alcohol or drug treatment programs.³ In San Francisco, only 16% of binge-drinking MSM have sought alcohol treatment, underscoring the need for novel alcohol interventions.¹⁸ MSM may be less likely to completely abstain from alcohol than heterosexual men,⁵² emphasizing the need to consider alternative treatment outcomes including reductions in drinking. **Despite the link between binge drinking and HIV risk, the use of pharmacologic interventions to reduce alcohol-intake or alcohol-related sexual risk among MSM is almost entirely unexplored.** The absence of published studies on efficacious interventions to reduce alcohol-related sexual risk behaviors among MSM who have no desire to abstain from alcohol **presents a major gap in the field of alcohol research and HIV prevention.** Pharmacotherapy trials for methamphetamine dependence and cocaine dependence in MSM have shown that reductions in substance use can result in parallel reductions in HIV-sexual risk behaviors among MSM not seeking treatment.^{53, 54} A pharmacologic intervention for binge drinking may lead to an analogous parallel reduction in alcohol-related sexual risks. **A critical challenge for HIV prevention interventions with MSM is the lack of interventions that reach MSM and effectively address HIV risk conferred through unprotected sex for MSM who binge drink.**

Naltrexone is an efficacious and effective pharmacologic treatment for alcohol dependence that blocks the reinforcing positive effects of alcohol use. Alcohol consumption results in the release of β -endorphins that bind and activate μ -opioid receptors.⁵⁵ Naltrexone competitively blocks β -endorphins from activating μ -opioid receptors⁵⁶ in the nucleus accumbens and ventral tegmental area, which mediate dopamine release (Figure 1, adapted from⁵⁷). Thus, the opioid antagonistic mechanism of action of naltrexone decreases the activity of the dopamine reward pathways,^{58, 59} tempering the positive neurobiological effects of alcohol.^{56, 60} **Naltrexone is effective in attenuating the positive subjective effects of alcohol intoxication—including quality of “high”, craving, and euphoria, supporting its efficacy among current drinkers.**⁶¹⁻⁶⁵ A two-year longitudinal study of “heavy social drinkers” who habitually binge drink found that the positive subjective and stimulant effects of alcohol are strong predictors of sustained and increased binge drinking.⁶⁶ **Given naltrexone’s efficacy in reducing the positive effects of alcohol that have been linked to future binge drinking,⁶⁶ naltrexone may be a promising option to reduce binge drinking.** Naltrexone is well-tolerated by active alcohol drinkers and has no known significant drug interactions.^{56, 67-70} Naltrexone has few serious side effects, no known abuse potential,^{68, 69, 71-74} and no known sexual side effects.⁷¹

Naltrexone’s pharmacokinetic properties support targeted administration (i.e., use in anticipation of heavy alcohol use on an “as needed” basis). Naltrexone’s activity is believed to be due to both the parent and the 6- β -naltrexol metabolite.⁷¹ Naltrexone reaches peak plasma levels

within one hour of oral administration. The mean elimination half-life for naltrexone and 6-β-naltrexol are four and 13 hours, respectively.⁷¹ Naltrexone also has high affinity to the μ-opioid receptor ($K_i = 2.5 \pm 0.21$ nM) and a single 50 mg dose can block μ-opioid receptors for up to 72 hours⁷⁵ raising the possibility that dosing even 1-2 days prior to anticipated alcohol consumption may be effective. **Targeted administration of naltrexone on an “as needed” basis has shown promise in reducing heavy drinking among heterosexuals.** Targeted naltrexone dosing was feasible and acceptable in a small pilot study of heavy-drinking young adults not ready or willing to abstain from alcohol; the trial completion and targeted medication adherence rates were 93% and 83%, respectively.⁷⁶ Other samples of non-dependent heavy drinkers have also been successfully recruited and retained in targeted dosing studies.^{11, 77-79} Targeted naltrexone administered after a period of daily dosing significantly reduced heavy-drinking relapse.⁸⁰ Similarly, in a trial conducted by Kranzler, et al., men assigned to targeted naltrexone showed significant reductions in mean drinks per day, and in number of drinks during drinking days, compared to those assigned to *daily* naltrexone administration, *daily* placebo, or targeted placebo.¹¹ Intermittent dosing schedules for opioid antagonists like naltrexone show similar results: targeted nalmefene reduced heavy drinking days, “very heavy” drinking days, and number of drinks during drinking days in randomized controlled trials.^{81, 82} None of these studies have evaluated sexual risk behaviors or exclusively recruited binge drinking MSM at risk for acquiring or transmitting HIV. **Questions about the efficacy of targeted naltrexone to reduce alcohol-related sexual risk behavior remain unanswered; no efficacy trial has determined if targeted use of pharmacologic agents for binge drinking can reduce HIV risk behavior.**

2 STUDY RATIONALE

Oral naltrexone was chosen because we believe it will be more acceptable to non-treatment seeking, non-alcohol dependent binge drinking MSM. Intermittent dosing makes sense for most binge-drinking MSM because data indicate that they do not binge drink daily. Injectable naltrexone's opioid blockade can last a month or more and overcoming the opioid antagonism with high opioid doses requires close monitoring and expert personnel.^{75, 132} Injectable naltrexone is also associated with more adverse events than oral naltrexone.^{132, 133} Oral naltrexone was specifically chosen because of its mechanism of action, and safety profile. Dilsulfiram is not ideal as it requires abstinence,¹³⁴ which may not be acceptable in our target population. Acamprosate has been shown to sustain abstinence, although not in intention-to-treat analyses in American studies¹³⁴ and thrice-daily dosing limits its utility.¹³⁴

Much like other chemoprophylaxis strategies, intermittent targeted dosing of oral naltrexone will not be acceptable to everyone. However, the fact remains that for most MSM, bars, clubs and other venues that serve alcohol remain the dominant setting for social interactions with other MSM.¹²⁻¹⁵ For MSM who are interested in reducing binge drinking but do not wish to isolate themselves from these venues, targeted dosing of oral naltrexone may be an attractive alternative. *Indeed, preliminary data from our ongoing pilot, the Project iN study, suggest that taking a medication to reduce alcohol consumption is feasible and acceptable among binge-drinking MSM.* If targeted dosing is efficacious among binge-drinking MSM, it may ultimately expand strategies for MSM to reduce their alcohol consumption.

2.1 Risk / Benefit Assessment

Adverse drug effects: A primary risk of participation in this study is the potential of AEs due to taking naltrexone. These risks are seen as reasonable, given the favorable side effect profile for this medication and the fact that we will exclude persons from the trial who are at higher risk for AEs. As part of the informed consent process, participants will be informed of the potential risks of taking naltrexone.

Naltrexone is well-tolerated and has no known significant drug interactions.⁵⁴ In randomized controlled trials, naltrexone has few serious side effects; it has no known abuse potential and dependence has not been reported.^{54, 66, 67, 69-72} Naltrexone's activity is believed to be due to both the parent compound and the 6-naltrexol metabolite.⁶⁹ The mean elimination half-life of for naltrexone and 6-naltrexol are four and 13 hours, respectively.⁶⁹ Initial trials evaluating the efficacy of naltrexone as treatment for alcohol dependence raised no safety concerns.^{65, 66} Naltrexone was also well-tolerated in subsequent studies in more clinically heterogeneous populations with co-morbid conditions.^{67, 112} Naltrexone has not been shown to cause significant increases in complaints in placebo-controlled trials in patients known to be free of opioids for more than 7 to 10 days.⁶⁹ The largest safety study to date on clinical use of naltrexone as a pharmacotherapy for treatment of alcoholism was a multi-center safety trial involving 865 individuals (500 naltrexone-treated patients, 238 patients in an unmedicated control group).⁶⁸ Results of this study demonstrated that the most commonly reported side effects were nausea (9.8%), headache (6.6%), dizziness (4.4%), nervousness (3.8%), and fatigue (3.6%); serious side effects were uncommon.⁶⁸ Naltrexone was discontinued in 15% of the participants, with nausea being the most common reason for medication discontinuation.⁶⁸ Studies in alcoholic populations and healthy volunteers have suggested that a small number of patients may experience an opioid withdrawal-like symptom complex including tearfulness, mild nausea, abdominal cramps, restlessness, arthralgia, myalgia, and nasal symptoms.⁶⁹ Naltrexone has no known sexual side-effects⁶⁹, supporting its potential acceptability for sexually-active MSM. Depression, suicidal ideation, and suicide attempts have been reported in both groups when comparing naltrexone and placebo for treatment for alcoholism.⁶⁹ There is no indication that naltrexone treatment increases the risk of suicide.⁶³

A review of the literature concluded that in patients treated for heroin or alcohol dependence, naltrexone does not cause clinically significant liver disease or exacerbate pre-existing liver disease.⁷¹ However, naltrexone has the capacity to cause hepatocellular injury in excessive doses and is contraindicated in acute hepatitis and liver failure.⁶⁹ Patients with these conditions will be excluded from our trial. Naltrexone is also contraindicated in patients who are currently dependent on opioids or in acute opioid withdrawal. The team anticipates that few participants will be excluded by virtue of current opioid use; for example, in our recently published mirtazapine study, only 7% of MSM met criteria for opioid dependence. Although the opioid blockade produced by naltrexone is surmountable, this situation requires careful medical management by trained personnel in settings equipped for resuscitation. Attempts by patients to overcome naltrexone's opioid antagonism may lead to an overdose. Naltrexone may also precipitate severe opiate withdrawal, including mental status change, nausea, vomiting, diarrhea, and dehydration in patients who are not opioid-free for a minimum of 7 to 10 days.⁶⁹ For this reason, urine opioid testing is needed to screen all potential participants for opioid use. Patients who have a foreseeable need for opioid pain management (e.g. potential elective surgery in the study period) will also be excluded. Additionally, all patients will be fully informed verbally and in the written consent form about the potential for overdose by attempting to overcome naltrexone's opioid antagonism.

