SUBJECT SELECTION CRITERIA	
Inclusion Criteria: (1) Male gender (2) self-reported anal sex with men in the prior three months while under the influence of alcohol (3) at least one binge drinking (five or more drinks on a single occasion) session per week in the prior three months; (4) interested in reducing binge alcohol consumption; (5) HIV-negative by rapid antibody test or medical record documentation of HIV infection (HIV positive participants); (6) no current acute illnesses requiring prolonged medical care; (7) no chronic illnesses that are likely to progress clinically during trial participation; (8) able and willing to provide informed consent and adhere to visit schedule; (9) age 18-70 years; (10) baseline CBC, total protein, albumin, glucose, alkaline phosphatase, creatinine, BUN, and electrolytes without clinically significant abnormalities as determined by study clinician in conjunction with symptoms, physical exam, and medical history.
 
Exclusion Criteria: (1) Any psychiatric (e.g. depression with suicidal ideation) or medical condition that would preclude safe participation in the study; (2) known allergy/previous adverse reaction to naltrexone; (3) current use of/ dependence on any opioids or a known medical condition which currently requires/may likely require opioid analgesics; (4) opioid-positive urine at enrollment; (5) current CD4 count < 200 cells/mm³ (6) moderate/severe liver disease (AST, ALT \geq 3 times upper limit of normal);

	(7) impaired renal function (creatinine clearance < 50 ml/min); (8) currently participating in another intervention research study with potential overlap; (9) alcohol dependence as determined by SCID criteria (participants with non-dependent alcohol use disorders/symptoms of alcohol abuse [per DSM-IV] are eligible) (10) any condition that, in the principal investigator and/or study clinician's judgment interferes with safe study participation or adherence to study procedures; (11) not having a cell-phone that can send and receive text messages.
TEST PRODUCT, DOSE, AND ROUTE OF ADMINISTRATION	Naltrexone HCL 50 mg (ReVia), oral administration as needed.
CONTROL PRODUCT, DOSE AND ROUTE OF ADMINISTRATION	Placebo 50 mg, oral administration as needed.

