6.3 Exclusion Criteria

- (1) Any psychiatric (e.g. depression with suicidal ideation) or medical condition that would preclude safe participation in the study;
- (2) known allergy/previous adverse reaction to naltrexone;
- (3) current use of/ dependence on any opioids or a known medical condition which currently requires/may likely require opioid analgesics;
- (4) opioid-positive urine at enrollment;
- (5) current CD4 count < 200 cells/mm³;

- (6) moderate/severe liver disease (AST, ALT \geq 3 times upper limit of normal);
- (7) impaired renal function (creatinine clearance $<$ 50 ml/min);
- (8) currently participating in another intervention research study with potential overlap;
- (9) alcohol dependence as determined by SCID criteria (participants with non-dependent alcohol use disorders/symptoms of alcohol abuse [per DSM-IV] are *eligible*)
- (10) any condition that, in the principal investigator and/or study clinician's judgment interferes with safe study participation or adherence to study procedures;
- (11) not having a cell-phone that can send and receive text messages;

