7.1 Allowed Medications and Treatments

Standard therapy is allowed except for naltrexone treatments and opioid medications as noted in the exclusion criteria described above and as noted in the prohibited medications section below.

Prohibited Medications and Treatments

The following medications are prohibited during the study and administration will be considered a protocol violation:

- 1) Opioid medications
- 2) Naltrexone treatments

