10 EVALUATIONS BY VISIT

10.1 VISIT 1 (SCREENING VISIT—WEEK 1)

Review the study with the subject (subject's legal representative) and obtain written informed consent and HIPAA authorization and assent, if appropriate.

Assign the subject a unique screening number.

Record demographics data.

Record medical history, including a history of mental health, sexual behaviors and substance use, diagnosis date, and prior Alcohol treatments.

Record concomitant medications.

Perform a complete physical examination.

Collect urine sample for alcohol, opiates, and other substances test. If capable of becoming pregnant then a pregnancy test. Record results.

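### No eligibility rule requires the 7 to 10 opioid-free days that the protocol's own risk section treats as the safety threshold for naltrexone

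*Combined protocol and SAP*

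**What the plan says.** The risk text in section 2.1 describes precipitated withdrawal (mental status change, vomiting, diarrhea, dehydration) as a danger "in patients who are not opioid-free for a minimum of 7 to 10 days". Its stated response is a test, not an interval: "For this reason, urine opioid testing is needed to screen all potential participants for opioid use". The same section calls the drug risk reasonable partly because "we will exclude persons from the trial who are at higher risk for AEs".

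The eligibility rules in section 6.3, repeated in the synopsis, contain two opioid criteria. Exclusion 3 covers "current use of/ dependence on any opioids or a known medical condition which currently requires/may likely require opioid analgesics". Exclusion 4 is "opioid-positive urine at enrollment". Neither gives a number of days, and the word current is not defined. Exclusion 10 lets the investigator or study clinician exclude any man with a condition that in their "judgment interferes with safe study participation or adherence to study procedures".

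During the study, section 7.1 bans opioid medications: "The following medications are prohibited during the study and administration will be considered a protocol violation". At Visit 1 (section 10.1) staff are to "Collect urine sample for alcohol, opiates, and other substances test", and section 10.3 repeats the urine test at enrollment, the visit at which study drug is handed out.

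**The concern.** The protocol names a serious harm and a threshold in days, then writes criteria that do not contain the threshold. Section 2.1 relies on the interval a second time: it reports no significant excess of complaints in placebo-controlled trials of patients known to be opioid-free for more than 7 to 10 days. Men inside that interval therefore fall outside the reassurance as well as inside the warning.

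What is at stake is participant safety, not the efficacy analysis. Whether a recent user is kept out depends on a urine window the protocol does not state and on how each clinician reads the word current. Doses are self-administered away from the clinic, and no minimum delay between enrollment and first dose is set.

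**Working it through.** **Step 1. Does any existing safeguard require 7 to 10 opioid-free days before the first dose?**

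- *Urine tests at Visit 1 and enrollment (10.1, 10.3).* No detection window is stated. Section 9.3.5.1 provides laboratory confirmation for positive screens only, so a negative is accepted as it stands.
- *30-day medication record (9.1.6).* It covers the right period but records medications, and it is not tied to an eligibility decision.
- *Ban on opioid medications (7.1).* It applies during the study and to medications.
- *Substance-use history (10.1).* Listed at Visit 1 only. Screening may last up to 30 days, so it can be that old at enrollment.
- *ACASI at enrollment (10.3).* Section 9.2.2 says staff will not see these data during the trial, so they cannot serve as a check.
- *Physical examination at enrollment (9.1.4).* No question on recent opioid use is specified.
- *Dispensing review (8.4.2).* It lists how to take the drug, side effects and pager access, not recent opioid use.
- *Exclusions 1 and 10 (6.3).* Discretionary, with no interval.

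None sets the interval. Because the record and the ban deal with medications, what remains is mainly recent use that is non-prescribed or judged not current.

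**Step 2. How large can the shortfall be?** The plan has no figure to reproduce, so this is a bound.

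Inputs:

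- L = opioid-free days named in section 2.1: 7 or 10.
- w = urine detection window in days. Not in the documents; assumed values 1, 2, 3, 5, 7 and 10.
- d = days from enrollment to first dose. No minimum is set, so d = 0 is the extreme case. Section 8.4.3 encourages at least 3 capsules a week and section 8.4.1 allows no more than one per 24 hours. A man who takes 3 in week 1 must therefore start by 168 − 48 = 120 hours, that is, d = 5.

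A negative enrollment urine implies at least w opioid-free days, taking the test as fully sensitive within its window. If there is no use after enrollment, the man has at least w + d opioid-free days at first dose, so

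shortfall ≤ max(0, L − w − d).

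For example, L = 10, w = 3, d = 0 gives 10 − 3 − 0 = 7 days.

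| L | d | w = 1 | w = 2 | w = 3 | w = 5 | w = 7 | w = 10 |
|---|---|---|---|---|---|---|---|
| 7 | 0 | 6 | 5 | 4 | 2 | 0 | 0 |
| 7 | 2 | 4 | 3 | 2 | 0 | 0 | 0 |
| 7 | 5 | 1 | 0 | 0 | 0 | 0 | 0 |
| 10 | 0 | 9 | 8 | 7 | 5 | 3 | 0 |
| 10 | 2 | 7 | 6 | 5 | 3 | 1 | 0 |
| 10 | 5 | 4 | 3 | 2 | 0 | 0 | 0 |

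The shortfall disappears once w + d reaches L, so a man who starts later than day 5 has less than the d = 5 rows show. The urine test alone guarantees the interval, whatever the dosing day, only if w is at least L.

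**The case against.** The best counter-argument is that the protocol does not contradict itself. Section 2.1 names a hazard and chooses urine testing as the control; exclusion 4 implements that control, and exclusion 3 removes current users and dependent men whatever the urine shows. A positive urine at Visit 1 would itself be evidence of current use. The medication record is not expressly limited to prescribed drugs, so a non-prescribed analgesic might be captured. Participants also get dosing training, labelled warnings, a wallet card and an emergency number. The remaining man is non-dependent, urine-negative and judged not to be a current user, and nothing in the documents shows how often such a man would have severe withdrawal. With 1:1 allocation, about half of any such men would receive placebo. The table counts days, not events. The proposed question relies on self-report and would miss a man who conceals use.

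Much of this stands. There is no broken promise, the exposed group is probably small, and the shortfall is not an estimate of harm. But none of these safeguards supplies the interval: labels and emergency contacts warn or help after the event, and they do not decide eligibility. A test with an unstated window cannot be shown to verify 7 to 10 days. Self-report will not catch concealment, but it will catch a man who would answer truthfully and is never asked. If clinicians already ask, writing the rule down makes the practice uniform and auditable. The consent pages are not in the public text, so any instruction there cannot be checked; it would not in any case be an eligibility criterion.

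**Conclusion.** The point holds. Under the criteria as written, a man with recent opioid use not regarded as current and a negative enrollment urine can be given naltrexone inside the period that section 2.1 identifies as dangerous. That conclusion rests on one assumption, that the urine window is shorter than 7 to 10 days. If so, the uncovered period is at most 9 days (L = 10, w = 1, dose on enrollment day). It shrinks with a longer window or a later first dose, and many combinations in the table give zero. The number of men affected and the number of withdrawal events cannot be derived from the documents. The gap does not touch the estimand, the analysis or the power. It should be corrected because the harm is serious by the protocol's own account and the remedy is cheap; confidence is medium because the window is unknown.

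**What to change.** Add one exclusion to section 6.3 and the synopsis: any opioid use, prescribed or not, within a fixed number of days before the first dose. Ten days is the cautious choice within the 7 to 10 named in section 2.1. Check it at the enrollment visit before drug is dispensed, through a direct question from the clinician as part of the section 8.4.2 review and a look at the 30-day medication record from section 9.1.6. Keep both urine tests, since the question alone cannot detect concealed use.

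The cost is one line of protocol text and one question per participant, with no new test. A few enrollments may be delayed or lost; a man who reports recent use can be re-checked once the interval has passed.
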